Administration of the trial drugs has to be stopped temporarily in case of a DLT (see [section 5.2.3](#)). Patients may continue therapy only after recovery from the DLT to CTCAE levels which allow further therapy and only with a reduced dose of BI 6727, the LD-Ara-C dose will remain unchanged. The new dose of BI 6727 must be finally agreed on between the clinical monitor of Boehringer Ingelheim and the investigator. The reduced dose will be valid for all following treatment cycles in the individual patient. A reduction of the dose will be allowed only once for an individual patient during the whole trial. In case, a patient experiences a second episode of DLT with the reduced BI 6727 dose, the treatment has to be

permanently discontinued. Likewise, treatment has to be discontinued in case the DLT is not reversible.

In this trial, an intrapatient dose escalation of BI 6727 will be allowed in the phase I part of the trial to increase the probability of clinical benefit. In case of a clinical response other than CR or CRI (i.e. PR or no change), the patient may receive a higher dose of BI 6727 provided that the drug is tolerated well (i.e. non-haematological drug related adverse events CTCAE grade ≥ 2 and haematological drug related adverse events CTCAE grade ≥ 3 unless preexistent). The BI 6727 dose escalation may be up to 50 mg/administration for both schedules. All decisions on intrapatient dose escalation will be made only in agreement between the investigator and the sponsor. Beginning after the first cycle of treatment, dose escalations may be repeated after every cycle and may in individual patients exceed the MTD found in this trial. A dose escalation must not be performed in patients who have achieved CR or CRI.

All changes of the BI 6727 dose will simultaneously affect both days of BI 6727 administration, i.e. BI 6727 dose will always remain the same on days one and fifteen.

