7.3.4 Interim analyses

Early analyses of response to therapy will be performed before completion of recruitment in order to support internal strategic decision making and planning for future clinical trials. In order to avoid bias of these early efficacy analyses on trial conduct, the results will not be distributed to trial sites before database lock for the CTR (see [section 6.2.3.3](#)). The analyses will be performed when approximately 50% of planned patients in the phase II part of the trial have either stopped treatment or completed at least two treatment cycles. Details of the early analyses of response to therapy will be specified in the interim trial statistical analysis plan. The early efficacy analyses will be documented and archived. If considered necessary for internal strategic decision making the early efficacy analysis may be repeated once when approximately 70% of planned patients in the phase II part of the trial have either stopped treatment or completed at least two treatment cycles.

After all patients of treatment schedule A that are contained in the full analysis set (phase I) have either completed at least one course of BI 6727 in combination with cytarabine or

dropped out of the study, a safety analysis will be performed. For this purpose a database snapshot will be performed. The safety analysis will summarize results regarding safety of the patients in the phase I part and will contain the determination of the MTD as well as a recommendation for the dose of BI 6727 to be used in the phase II part of the study. The selection of the recommended dose for the phase II part will consider overall safety observed during all treatment cycles. No efficacy comparisons will be performed in this phase I safety analysis. Detailed specifications of the phase I safety analysis are provided in the TSAP. The phase I safety analysis will be documented and archived.

For other safety purposes database snapshots can be performed as deemed appropriate.

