6.1.3 Specification of treatments for analyses

Table 6.1.3: 1 Definition of the label of the analysing treatment period, analysis numbers, and the labels using for displaying in the tables, start date and end date.

Label of the "ATP" (ANALLBL)	Analysis number (ANALNO)	Label for the columns displayed in the tables (NWTRCD)	Start date	End date
Screening	5	Actual treatment (atrcd) ²	Date of informed consent	Start date of first treatment in course 1
Course 1 analysis	4	Initial treatment schedule ¹	Start date of first treatment in course 1	Start date of first treatment in course 2 or start date of the actual treatment "post-study"
Course 1 analysis	4	Total	Start date of first treatment in course 1	Start date of first treatment in course 2 or start date of the actual treatment "post-study"
All course analysis	3	Initial treatment schedule ¹	Start date of first treatment in course 1	Start date of actual treatment "post-study"
All course analysis	3	Total	Start date of first treatment in course 1	Start date of actual treatment "post-study"
Post-study	7	Initial treatment schedule ¹	Start date of actual treatment "post-study"	Date of Data Base Lock + 1 day

¹- use treatment specification of the initial treatment schedule defined in [Table 6.1.2: 1](#) and column 'Format for TPATT'

²- use treatment specification of the actual treatment defined in [Table 6.1.1: 1](#)

Note that death or lost to follow-up automatically ends the currently ongoing analysing treatment period for a patient.

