7.7.1 Adverse events

The analyses of adverse events will be descriptive in nature and will be based on BI standards (see [\[3.1\]](#)). Adverse events will be coded with the most recent version of MedDRA. According to the BI standards, multiple occurrences of adverse events are collapsed to episodes if time overlapping or adjacent (maximal one day) on the MedDRA lowest level term and multiple episodes will be condensed to records on the preferred term and SOC level.

AEs as well as DLTs will be evaluated both for all courses as well as for first course only (in the phase I part).

The analysis of adverse events will be based on the concept of treatment emergent adverse events. Adverse events will be distinguished for the period in which the subjects are under study drug (on-treatment) as well as for screening, and post-study (For details on the analysing treatment period, see section [6.1.3](#)). If applicable, the actual dosage of BI 6727 administered on the day each adverse event starts will also be derived and will be included in the listing. The system organ classes will be sorted according to the standard sort order specified by EMEA, PTs will be sorted alphabetically (within SOC).

All patients will be reported in the summary tables under the initial treatment group (randomised treatment) including the initial treatment schedule.

AEs with onset date at Screening- and Post-study-period (as defined in [Table 6.1.1: 1](#)) will be displayed in two separate listings. Listings of screening events will not be sorted by initial treatment ([Table 6.1.2: 1](#)). But post-study listings will be sorted by initial treatment.

AE flags and attributes

An AE flag will be defined for patients who developed an AE that was CTCAE grade ≥ 3 , DLT, or serious AE.

An AE attribute "CTCAE grade 3/4 or 5 combined with drug relation" will be derived to avoid incorrect condensing. Consider, for instance, a patient with coincident drug-related abdominal pain with CTCAE 1, and non-related vomiting with CTCAE 3. Without the new attribute these AEs would be reported as drug-related Grade 3/4 under the SOC Gastrointestinal disorder. With the new AE attribute these AE would not be reported under that category.

The number of patients with DLT will be listed per treatment group with the respective events fulfilling the criteria for DLT.

A separate listing for all patients who developed AEs with CTCAE grade ≥ 3 , DLT, and serious AEs will be generated.

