Incidence and intensity of adverse events

The overall incidence and intensity of adverse events, as well as relatedness of adverse events to treatment with BI 6727 will be reported for all treatment schedule arms.

Serious adverse events will be tabulated. In addition, Events leading to dose reduction or treatment discontinuation will be examined, but may not be reported as individual tables, depending upon the extent of overlap with the occurrence of DLT.

For the phase I part only, the dose-toxicity relationship will be examined descriptively and inferentially, using DLTs in treatment course 1 and DLTs up to the end of the on treatment phase, in separate analyses. Further, the time to first DLT will be explored descriptively in all dose groups, and Kaplan-Meier plots based upon the MTD group will be presented.

As a first step, for each time period, the number of DLTs that a patient has will be summarised. If the majority of the patients have either 0 or 1 DLT, then a simple logistic regression will be calculated. If however, there are quite a few patients with >1 DLT, then a proportional odds model will be used.

With this logistic regression, a model including only the BI 6727 dose (and intercept) will be used. Hence, by back-transformation of the logit model, the probability (and 95% confidence interval) of a DLT in this time period will be presented on a graph together with the dose. The dose corresponding to a 25% probability of a DLT in the time period will be indicated and the p-values for the intercept and slope of this model will also be included in the footnote. Additionally the expected toxicity level for the dose chosen in phase II will be provided.

Finally, the time on treatment prior to the first DLT will be presented graphically together with the dose. Different symbols will be used for patients with (filled dot) and without (unfilled dot) a DLT. Using the MTD group, the Kaplan Meier plot estimating the probability of an event over time will be presented.

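### The all-course DLT model has one BI 6727 dose per patient, most likely the starting dose, although phase I patients may be escalated after every cycle

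*SAP*

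**What the plan says.** SAP 7.7.1 (Incidence and intensity of adverse events) examines the phase I dose-toxicity relationship "using DLTs in treatment course 1 and DLTs up to the end of the on treatment phase, in separate analyses". For the model it says: "With this logistic regression, a model including only the BI 6727 dose (and intercept) will be used". For each period the output is the DLT probability by dose, the dose at 25% DLT probability, and the expected toxicity at the dose taken into phase II. A Kaplan-Meier plot of time to first DLT is drawn for the MTD group.

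Protocol 4.1.4 allows intrapatient escalation in phase I, by up to 50 mg per administration from the end of cycle 1: "dose escalations may be repeated after every cycle and may in individual patients exceed the MTD found in this trial". It is closed to patients in CR or CRi, requires good tolerability, and needs agreement between investigator and sponsor.

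On which dose counts, SAP Table 6.1.3: 1 labels both the course-1 and the all-course analysis by initial treatment schedule, with the footnote "use treatment specification of the initial treatment schedule defined in" Table 6.1.2: 1. SAP 7.7.1 adds: "All patients will be reported in the summary tables under the initial treatment group (randomised treatment) including the initial treatment schedule". It also says that "the actual dosage of BI 6727 administered on the day each adverse event starts will also be derived", but the only stated use is a listing.

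**The concern.** In course 1 each patient has one dose level, so one dose term is enough. Over all courses a patient may have had several. If the starting dose is entered, a patient who starts at 150 mg and has a DLT in course 4 at 300 mg counts as a DLT at 150 mg. Toxicity produced at higher doses then raises the fitted risk at lower ones. The slope flattens and the 25%-DLT dose moves down.

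The result would be read as the risk of repeated courses at a given dose, which is what phase IIa patients receive, since intrapatient escalation is limited to phase I. The Kaplan-Meier plot has the same problem, because it can include time above the MTD. Later-course safety also has a use: Protocol 7.3.3 treats the all-cycle safety analysis as support for the MTD, and Protocol 7.3.4 says "The selection of the recommended dose for the phase II part will consider overall safety observed during all treatment cycles".

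**Working it through.** **Figures in the plan.** No stated figure depends on this model. The nearest DLT figures are in Protocol Table 7.6: 1, from 1 − (1−p)^6 − 6p(1−p)^5. At p = 0.40, 0.42 and 0.45 this gives 0.7667, 0.7965 and 0.8364, which match the stated 0.77, 0.80 and 0.84. The planned phase I size also reproduces: (5 + 2) × 3 = 21 per schedule.

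**Inputs.** From the documents: the 50 mg step, possible after each cycle (Protocol 4.1.4), and a logistic model with dose and intercept only (SAP 7.7.1). The documents give no DLT risk by dose, continuation rate or escalation frequency, so these are assumptions.

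**Hand example.** Assume per-course DLT risks of 2, 4, 7 and 12% at 150, 200, 250 and 300 mg. For a patient starting at 150 mg, over four courses:
- escalated every course: 1 − 0.98 × 0.96 × 0.93 × 0.88 = 0.230
- constant 150 mg: 1 − 0.98^4 = 0.078

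A model on starting dose records the first figure at 150 mg.

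**Simulation 1.** The risks above, continued as 20, 30, 40 and 50% at 350 to 500 mg and held at 50% beyond. Starting doses are 150 to 400 mg, 60% continue after each course, there are at most six courses, and observation ends at the first DLT. Escalation is random among continuers. Any DLT is regressed on starting dose.

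| Escalation at each continued course | 25%-DLT dose | Fall | Slope per 50 mg | DLTs above starting dose |
|---|---|---|---|---|
| 0% | 302 mg | – | 0.61 | 0% |
| 20% | 290 mg | 12 mg | 0.58 | 22% |
| 50% | 272 mg | 30 mg | 0.52 | 43% |
| 100% | 239 mg | 63 mg | 0.45 | 63% |

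Repeat runs agree within about 3 mg.

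**Simulation 2.** A different risk curve, logit-linear through 5% at 150 mg and 25% at 350 mg, with up to eight courses. The 25%-DLT dose on starting dose, in mg:

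| Continuation | Later-course risk | 0% | 20% | 50% | 100% | Fall |
|---|---|---|---|---|---|---|
| 40% | unchanged | 294 | 288 | 281 | 267 | 6–27 |
| 60% | unchanged | 252 | 241 | 219 | 187 | 11–65 |
| 40% | halved | 318 | 316 | 310 | 300 | 2–18 |
| 60% | halved | 290 | 281 | 268 | 244 | 9–46 |

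With 60% continuation and unchanged risk, the any-DLT rate in patients starting at 300 mg rises from 0.34 without escalation to 0.37, 0.39 and 0.43. The course-1 model stays at 349 to 351 mg in every scenario.

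**Testing the remedies.**
- *Patient-course model on the dose given.* In simulation 2 with unchanged later-course risk it returns about 350 mg and a slope of 0.46 to 0.47, as it should. Under the simulation 1 risks with later-course risk halved, it gives 419 to 469 mg without a course term, against about 377 mg for the true course-1 curve. With a term for course 1 versus later courses it gives 379 to 391 mg.
- *Any-DLT model per patient, cut at first escalation.* Under simulation 1 the 25% dose rises from 302 mg to between 322 and 378 mg, because follow-up is shortened. This is not a clean remedy.

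**The case against.** The strongest objection is that SAP 7.7.1 never says the model uses the starting dose. The initial-treatment rule is written for summary tables and analysis labels, and the protocol's own equation of regimen with initial dose (7.3.3) belongs to the first-cycle analysis. That is correct, so the starting-dose reading is an inference, though the likeliest one. Other readings do not rescue the plan: last or maximum dose conditions on having tolerated earlier courses, and an undefined covariate leaves the choice until the data are seen.

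A reader might infer that the whole dose-toxicity result is wrong. The documents do not support that. The MTD uses first-cycle data only (Protocol 5.2.4), the course-1 model precedes any escalation, and SAP 3.3 calls all analyses descriptive and exploratory.

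A reader might also infer that the phase II dose is chosen from this curve. Protocol 2.1 and 7.3.4 refer to the MTD and overall safety and do not name the model. The supportive all-cycle analysis in Protocol 7.3.3 pools phase I and phase II patients, whereas this regression is phase I only. The SAP reports expected toxicity for a dose already chosen. SAP section 9.5, cited for the safety update, is not in the text available, so its use there cannot be checked.

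Further points stand:
- Full escalation is an upper bound, given the limits in Protocol 4.1.4.
- The shift lowers the estimated 25%-DLT dose, which is the cautious direction.
- With 21 patients spread over 150 to 400 mg (an assumed spread) and no escalation, the fitted 25% dose already runs from about 208 to 422 mg (5th to 95th percentile). Sampling error exceeds the bias.
- Dose changes are visible elsewhere: SAP 5.3.2 counts patients with an escalation or reduction, and SAP 7.1 lists dose changes.

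These points limit the weight of the finding. They do not make the all-course curve describe constant dosing.

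**Conclusion.** The point holds for the all-course model and the MTD-group Kaplan-Meier plot only. The dose covariate is undefined for patients whose dose changes. On the likeliest reading, the all-course slope is too flat, the 25%-DLT dose too low, and the toxicity expected at the phase II dose too high for constant dosing.

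The size cannot be taken from the documents. With 60% continuation and unchanged later-course risk, the 25%-DLT dose falls by about 10 to 30 mg at 20 to 50% escalation and by about 60 mg if every continuer escalates. It falls less with lower continuation or lower later-course risk, and not at all without escalation. These figures assume random escalation and no dose reductions. Reductions after a DLT would charge repeat DLTs to too high a dose, which matters mainly if the SAP's proportional odds variant is used.

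The analysis is exploratory, but its output would be mislabelled and the repair is cheap, so it should be made.

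**What to change.** In SAP 7.7.1:
1. Keep the course-1 model by initial dose.
2. For all courses, fit a patient-course model on the BI 6727 dose given in that course, with a term for course 1 versus later courses and standard errors clustered by patient. State that its 25% dose is a per-course figure. Risk over several courses at constant dose follows as one minus the product of the per-course probabilities of no DLT.
3. If a starting-dose version is kept, label it *DLT risk by starting dose, including later dose changes*.
4. Censor the MTD-group Kaplan-Meier plot at first intrapatient escalation. Any regression cut at escalation should also be at patient-course level, so that shorter follow-up is accounted for.

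The cost is SAP wording and modest programming. SAP 5.3.2 already sums administered BI 6727 dose per course.

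The SAP should state the limits. Dose and course are partly confounded. Escalated patients are those who tolerated earlier courses, so censoring at escalation may be informative. With about 21 patients per schedule, both the estimates and the clustered standard errors are imprecise.

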4.1.4 Selection and timing of doses for each patient

Prior to inclusion of a new patient in the phase I part the investigator has to confirm the actual dose tier of BI 6727 for the patient with the clinical monitor of the sponsor who oversees the dose escalation steps according to the safety data of patients from all trial sites.

BI 6727 will be administered as an intravenous infusion under the supervision of the investigator or designated personnel. Subcutaneous cytarabine injections will be administered according to the SPC.

The trial drugs may be administered at any time during the day. In case the second dose of BI 6727 is missed for administrative reasons the respective dose will be administered on the following two days. In case a dose of cytarabine is missed for administrative reasons the respective dose will not be administered at a later time (any missed cytarabine dose must be documented in the eCRF).

At the end of each treatment cycle, the response to treatment will be assessed. To continue treatment with further cycles, the following criteria must be met:

- 1.) Absence of disease progression (see [section 5.1.1](#))
- 2.) Neutrophils $\geq 500 / \mu\text{L}$ ($0.5 \times 10^9 / \text{L}$) and platelets $\geq 25,000 / \mu\text{L}$ ($25 \times 10^9 / \text{L}$); unless CTCAE grade 4 neutropenia or thrombopenia was preexistent
- 3.) Acceptable tolerability (in case of DLT, patients may continue therapy only after recovery from DLT to CTCAE levels which allow further therapy and only with a reduced dose), and recovery from drug-related cardiac toxicity.

In case criterion 2 is not fulfilled, the peripheral blood should be re-evaluated for up to three weeks. As soon as criterion 2 is met the treatment should be continued (unless other criteria for discontinuation or withdrawal apply, see [section 6.3](#)). A delay of haematopoietic reconstitution (i.e criterion 2 unmet) for more than three weeks after the end of the treatment cycle qualifies for DLT in patients with CRi or PR (see [section 5.2.3](#)). Any case of a delay in treatment cycle should be communicated to the clinical monitor of Boehringer Ingelheim. Progressive disease will lead to discontinuation of treatment.

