300+Cy20	AG	Date of first administration of either BI 6727 300 mg d1 + 15 or Cytarabine 20 mg d1-10	Time of first administration of either BI 6727 300 mg d1 + 15 or Cytarabine 20 mg d1-10
350+Cy20	AI	Date of first administration of either BI 6727 350 mg d1 + 15 or Cytarabine 20 mg d1-10	Time of first administration of either BI 6727 350 mg d1 + 15 or Cytarabine 20 mg d1-10
400+Cy20	AK	Date of first administration of either BI 6727 400 mg d1 + 15 or Cytarabine 20 mg d1-10	Time of first administration of either BI 6727 400 mg d1 + 15 or Cytarabine 20 mg d1-10
Cy20	W	Date of first injection of Cytarabine 20 mg d1-d10	Time of first injection of Cytarabine 20 mg d1-d10

Short label (REGSHNM in E_REG) unblinded	Sort order (SORTREG in E_REG)	Start date (CRF)	Start time (CRF/ derived)
Post-trt	X	For BI 6727 monotherapy: Date of last administration	For BI 6727 monotherapy: Stop time of last administration + 1min.
		For BI 6727 combi with Cytarabine or Cytarabine mono: Date of last administration of BI 6727 or Cytarabine whichever is later	For BI 6727 combi with Cytarabine or Cytarabine mono: Time of last administration + 1min.
Post-study	Y	Date of last administration of trial medication (last treatment course) + 21 days.	0:00:00

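### The Kaplan-Meier plot of time to first DLT (SAP 7.7.1) has no stated censoring rule and, if death and stopping are censored, can exceed the DLT probability it is said to estimate

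*SAP*

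**What the plan says.** SAP 7.7.1 (incidence and intensity of adverse events) examines DLTs in the phase I part over two windows, "using DLTs in treatment course 1 and DLTs up to the end of the on treatment phase, in separate analyses". It plans three kinds of output:

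- **Logistic regression on dose**, for each window: "the probability (and 95% confidence interval) of a DLT in this time period will be presented on a graph together with the dose".
- **Time to first DLT**: "the time to first DLT will be explored descriptively in all dose groups, and Kaplan-Meier plots based upon the MTD group will be presented". The section closes with the statement "Using the MTD group, the Kaplan Meier plot estimating the probability of an event over time will be presented".
- **A dot plot by dose**: "Finally, the time on treatment prior to the first DLT will be presented graphically together with the dose", with different symbols for patients with and without a DLT.

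Four other places determine when a first DLT can still be counted:

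- Protocol 4.1.4: "Progressive disease will lead to discontinuation of treatment". Protocol 6.3 repeats this as a discontinuation criterion.
- SAP 6.1.3: "Note that death or lost to follow-up automatically ends the currently ongoing analysing treatment period for a patient".
- SAP 6.1.1 starts the post-study period at "Date of last administration of trial medication (last treatment course) + 21 days". Under SAP 7.7.1, adverse events starting in that period go to a separate listing.
- Protocol 5.2.3 requires a non-haematological DLT to be drug related.

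**The concern.** Kaplan-Meier treats a censored patient as someone who could still have the event and whose later risk equals that of the patients still under observation. A patient who has died cannot have a DLT. A patient who has stopped trial drug for good, and whose 21-day window has closed, cannot have one that counts as on treatment. For a statement about how many patients experience a DLT, these are competing events and not ordinary censoring.

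With such patients censored, the curve answers a different question: what the DLT risk would be if nobody stopped, assuming that stopping is unrelated to the risk of a DLT. The SAP states neither the condition nor the assumption, and calls the curve an event probability.

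This is the only planned curve of DLT probability over time at the MTD. Protocol 2.1 and 7.3.4 say that safety beyond the first cycle is considered when the phase II dose is recommended. A reader of the phase I safety analysis could therefore see two different all-course DLT probabilities for the same patients, without an explanation of the gap.

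**Working it through.** **The plan's own DLT figure.** No all-course DLT probability is stated. The nearest figure is protocol Table 7.6: 1, the chance of two or more DLTs in six patients, 1 − (1−p)^6 − 6p(1−p)^5. For p = 0.40, 0.42 and 0.45 this gives 0.767, 0.797 and 0.836, which agree with the stated 0.77, 0.80 and 0.84.

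**Direction.** Let d_k be the DLT risk in cycle k among those at risk, and c the chance per cycle of leaving by progression, death or another stop without a DLT.

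- One minus Kaplan-Meier, stops censored: Σ KM(k−1)·d_k = 1 − Π(1−d_k), where KM falls only at DLTs.
- Cumulative incidence (Aalen-Johansen): Σ S(k−1)·d_k, where S falls at DLTs and at stops.

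Since KM(k−1) ≥ S(k−1), the first is never below the second. They are equal when no DLT follows a stop.

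**Inputs.**

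- Course-1 DLT risk 1/6, the largest observed proportion that the MTD definition allows (protocol 5.2.4, 7.6.1).
- Four cycles, taken from protocol 6.2.3.3. That sentence concerns phase II, so its use here is an assumption.
- Assumed, because the documents give no values: c from 10% to 50% per cycle, and the DLT risk after cycle 1.

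**Results at four cycles.**

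| DLT risk after cycle 1 | 1 − KM | Cumulative incidence, c = 10% / 30% / 50% | Excess |
|---|---|---|---|
| 1/6 per cycle | 51.8% | 45.6% / 35.4% / 27.7% | 6 to 24 points |
| 5% per cycle | 28.6% | 26.4% / 22.8% / 20.2% | 2 to 8 points |
| none | 16.7% | 16.7% / 16.7% / 16.7% | 0 |

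The first row with c = 30%: 1 − (5/6)^4 = 0.518. Survival per cycle is (5/6)(0.7) = 0.5833, so the cumulative incidence is (1/6)(1 + 0.5833 + 0.3403 + 0.1985) = 0.354.

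**Small cohort.** In 20,000 simulated cohorts of six with c = 30%, the mean estimates are 49.5% against 35.4% (first row) and 27.7% against 22.7% (second row). One concrete cohort of six: one DLT in cycle 1, then three patients stop, then one DLT among the two left. One minus Kaplan-Meier is 1 − (5/6)(1/2) = 58.3%, while 2/6 = 33.3% of patients had a DLT.

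**Cycle 1.** The model places stops at the end of each cycle, so it shows no excess in cycle 1. If stops also occur during the cycle, a small excess appears. With constant hazards, a DLT risk of 1/6 and stopping of 10% to 40% per cycle, 16.7% compares with 15.8% to 13.2%. This can arise because the phase I treated set keeps patients who were replaced (SAP 6.3), and protocol 6.3 replaces some patients who did not complete a cycle.

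**A longer horizon adds little.** With a constant 10% DLT risk and 40% stopping per cycle, continuous-hazard formulas give 27.1% against 14.4% at three cycles and 46.9% against 16.7% at six. By then only (0.9 × 0.6)^6 = 2.5% of patients remain at risk, so the six-cycle gap should not be relied on.

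**The case against.** The strongest reply has four parts.

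1. **The all-course DLT probability is already estimated without censoring.** The logistic regression uses each patient's DLT status and keeps early stoppers in the denominator. The expected toxicity at the phase II dose is announced alongside that model, and patients with DLT are also listed by treatment group. This stands. A reader might infer that the all-course DLT probability as such is overstated, but the documents support that only for the Kaplan-Meier curve.

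2. **The censoring rule is unknown.** The time-on-treatment wording belongs to the dot plot. SAP section 9.5, to which the introduction refers for the phase I safety update, is not in the available text. If event-free patients were kept at risk to the end of the window, the curve would equal the crude proportion. This stands, and it makes the excess conditional. It also leaves a choice that changes the result unspecified where the plot is described.

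3. **A DLT is not impossible once drug stops.** Events within 21 days of the last dose still count as on treatment, protocol 5.2.1 requires later related events to be reported, and protocol 5.2.3 judges haematological DLT in patients with CRi or PR up to three weeks after the cycle ends. This stands. Only death is an absolute bar; discontinuation bars a countable on-treatment DLT only after the window closes.

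4. **DLT risk while on drug is a legitimate tolerability quantity.** It does not depend on the stopping rate, and cumulative incidence would make a schedule with faster progression look safer. This is fair under independent censoring, but the SAP neither labels the curve that way nor states the assumption.

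A reader might also infer that the MTD or the phase II dose is distorted. Protocol 5.2.4 bases the MTD on the first cycle only. Protocol 2.1 and 7.3.4 refer to overall safety across cycles without naming this plot. Nor is a comparison of these curves between schedules planned.

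**Conclusion.** The point holds as a minor one about a single descriptive plot. As described, the curve lacks a censoring rule and a competing-risk method. If patients who die or permanently stop are censored, it equals or exceeds the actual cumulative probability of a DLT. The direction follows from the formulas. The size rests on assumed stopping rates and late DLT risks: 0 to about 24 points at four cycles, and nil if all DLTs come before the stops. The first-cycle MTD determination and the logistic-regression DLT probability are unaffected, and no decision rule uses the plot.

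**What to change.** In SAP 7.7.1, present the Aalen-Johansen cumulative incidence of first on-treatment DLT in the MTD group. Treat death and permanent discontinuation without a DLT as competing events, counting discontinuation once the 21-day window has closed. Censor only patients still on treatment at the data cut. If the Kaplan-Meier plot is kept, label it as DLT risk conditional on remaining on treatment and state its censoring rule.

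The cost is a few sentences in the SAP and one extra standard analysis, with no new data. With six patients at the MTD, either curve will be very uncertain.
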